### **Pre-filled Syringe**

- With your other hand, gently squeeze an area of the cleaned area of skin and hold it firmly.
- You will inject into this raised area of skin. Hold the syringe like a pencil at about 45° angle (see picture) to the skin.
- With a quick, short, “dart-like motion”, push the needle into the skin.
- After the needle is in, let go of the skin. Pull back slightly on the plunger. If blood appears in the syringe it means that you have entered a blood vessel. Do not inject adalimumab. Pull the needle out of the skin and repeat the steps to choose and clean a new injection site. Do not use the same syringe. Dispose of it in your special sharps container. If no blood appears, slowly push the plunger all the way in until all of the adalimumab is injected.
- When the syringe is empty, remove the needle from the skin keeping it at the same angle it was when it was pushed into the skin.
- Press a cotton ball or gauze pad over the injection site and hold it for 10 seconds. Do not rub the injection site. You may have slight bleeding. This is normal.
- Dispose of the syringe right away into your special sharps container.

3.0 Introduction

This analysis plan describes the statistical analyses to be completed for Study Protocol W14-406 dated 22 April 2016, which incorporates protocol Amendments 1 and 2.

This statistical analysis plan (SAP) provides details to further elaborate statistical methods as outlined in the protocol and describes analysis conventions to guide the statistical programming work. Pharmacokinetics analysis will be described in separate documents.

The SAP will be signed off before the study database is locked. Analyses will be performed using SAS® version 9.4 (SAS Institute, Inc., Cary, NC 27513) or higher on a Hewlett Packard workstation using the UNIX operating system.

4.0 Study Objectives, Design and Procedures

4.1 Objectives

The primary objective of this study is to determine the proportion of primary and secondary sub-optimal responders to adalimumab (ADA) monotherapy (sub-optimal responders defined as subjects with an unsatisfactory response to treatment based on investigator assessment) with a PGA ≥ 3 and a PASI ≥ 5 who have a satisfactory response (defined as highly or completely satisfied with subject's therapy using the satisfaction questionnaire) after 16 weeks of treatment with adalimumab and methotrexate (ADA/MTX) combination therapy, based on investigator and subject satisfaction assessments.

The secondary objective of this study includes:

- To determine the proportion of primary and secondary sub-optimal responders to ADA monotherapy (sub-optimal responders defined as subjects with an unsatisfactory response to treatment based on investigator assessment) with a PGA ≥ 3 and a PASI ≥ 5 who reach PASI 50, PASI 75 and PASI 90 16 weeks after initiation of ADA/MTX combination therapy.

- To define the demographic and clinical profile of subjects benefiting from ADA/MTX combination therapy.
- To determine the magnitude, timing, and maintenance of the benefit of adding MTX to ADA by assessing investigator/subject satisfaction with treatment, PGA, PASI, and Dermatology Life Quality Index (DLQI) at 8, 16, and 24 weeks after addition of MTX to therapy.
- To determine change in DLQI from baseline in subjects initiated on ADA/MTX treatment.
- To determine change in serum levels of ADA following addition of MTX and to characterize a possible correlation with changes in investigator/subject satisfaction with treatment, PGA, PASI and DLQI over the study period. Serum levels will be evaluated at baseline (initiation of ADA/MTX) and at Weeks 8, 16 and 24.

4.2 Design Diagram

[figure not shown]
This is a multicenter, single arm, open label longitudinal study. The study entails a screening period up to 35 days, a 24-week treatment period and a 70-day safety follow-up period.

At screening, subjects who provide written consent will complete a satisfaction questionnaire. PGA and PASI will be determined, and inclusion/exclusion criteria will be assessed. Data collected at a screening visit will include: subject demographics, disease history, vital signs, laboratory investigations and PGA, PASI and DLQI scores.

A 24-week single arm, open label treatment period during which subjects are treated by ADA/MTX. Starting at the baseline visit (Day 0), subjects will continue to self-administer ADA (40 mg eow) and will have oral MTX added to their treatment at a dose to be defined by the investigator (between 10 mg and 25 mg per week). All subjects will also receive the non-investigational medicinal product oral folic acid as a dietary supplement since MTX acts as a folic acid antagonist. The folic acid tablets will be provided by the investigator at a dose of 1.0 mg per day. The required folic acid dose

must be taken every day of the week except on the day when MTX is taken. The investigator will provide specific instructions on the number of folic acid tablets each subject should take. At site Visits 8, 16 and 24 weeks after initiation of ADA/MTX, the following parameters will be assessed: investigator assessment of disease status (using a satisfaction questionnaire); subject self-assessment of disease status (using a satisfaction questionnaire); PGA; PASI; DLQI; AEs; serum levels of ADA. A schematic of the study design is shown in [Figure 1](#):

Figure 1. Study Design Schematic

The 70-day safety follow-up period begins from the last dose of ADA, except those subjects that continue on ADA therapy after the end of study participation. Subjects will be discontinued from the study if they withdraw consent or if they are deemed unsuitable to continue for any reason by the investigator in consultation with the AbbVie Medical Monitor.

4.3 Sample Size

This study was planned to have a 30 month recruitment period where it was anticipated that approximately 200 subjects will be recruited. With this sample size the proportion of responders, defined as the proportion of subjects with a highly or completely satisfied response after 16 weeks of ADA/MTX therapy, based on an investigator assessment and subject self-assessment, can be estimated within $\pm 4.9\%$ with 95% confidence when the point estimate is 15%, within $\pm 6.4\%$ with 95% confidence when the point estimate is 30%, or within $\pm 6.9\%$ with 95% confidence when the point estimate is 50%. Additional accuracy estimates are provided in the table below.

Table 1. Accuracy Estimates with a Sample Size of 200 Subjects

Estimated Proportion of Responders (%)	Accuracy Estimate (%)
5	3.0
10	4.2
15	4.9
20	5.5
25	6.0
30	6.4
35	6.6
40	6.8
45	6.9
50	6.9

Note: Proportion of responders can be estimated with \pm accuracy with 95% confidence. The size of the 95% Confidence Interval would be $2 \times$ Accuracy.

Due to the enrollment plan change (enroll 50 patients or as the number of enrollment by 31 December 2016), updated accuracy estimates with a sample size of 50 subjects, about the proportion of subjects with a highly or completely satisfied response after 16 weeks of ADA/MTX therapy based on an investigator assessment and subject self-assessment, are provided in the table below.

Table 2. Accuracy Estimates with a Sample Size of 50 Subjects

Estimated Proportion of Responders (%)	Accuracy Estimate (%)
5	6.0
10	8.3
15	9.9
20	11.1
25	12.0
30	12.7
35	13.2
40	13.6
45	13.8
50	13.9

Note: Proportion of responders can be estimated with \pm accuracy with 95% confidence. The size of the 95% Confidence Interval would be $2 \times$ Accuracy.

4.4 Interim Analysis

No interim analysis is planned for this study.

5.0 Analysis Populations

5.1 Definition of Analysis Populations

Intent-to-Treat (ITT) Populations

The Intent-to-Treat population will be used for all efficacy analyses, which is defined as all subjects who receive at least one dose of study ADA and at least one dose of MTX during the study.

The primary efficacy analyses will also be conducted for the following sub-populations:

- ITT Subjects who are defined as primary sub-optimal responders at baseline based on Investigator assessment.
- ITT Subjects who are defined as secondary sub-optimal responders at baseline based on Investigator assessment.

Safety Populations

The Safety Population will be used for all safety analysis, which is defined as all subjects who received at least one dose of study ADA and one dose of MTX during the study. In this study, the safety population is the same as the ITT Population.

Notations for Treatment Groups

- ADA/MTX: Subjects who received ADA and MTX as study drugs.

6.0 Analysis Conventions

6.1 Definition of Baseline

The last non-missing measurement collected on or before the maximum date of either the first dose of ADA or the first dose of MTX will be used as baseline for the summary of demographics and disease characteristics, the safety analyses, and the efficacy analyses.

6.2 Definition of Final Observation

Final observation is defined as the last non-missing observation collected within 70 days following the last dose of study ADA.

6.3 Definition of Rx Days (Days Relative to the First Dose of Study Drug)

We define the maximum date of either the first dose of study ADA or the first dose of MTX during the study as Rx Day 1 (RxDY 1). Other Rx days (RxDY) are calculated for each time point as the number of days between Rx Day 1 and the specific time point. Rx

days are positive values when the time point of interest is after Rx Day 1. Rx days are negative values when the time point of interest is prior to Rx Day 1. For example, the day prior to Rx Day 1 is defined as Rx Day –1 (there is no Rx Day 0). Rx days will be calculated and displayed in all presentations of data in listing format.

6.4 Definition of Analysis Windows and Data Handling Conventions

All time points and corresponding time windows are defined based on Rx Days.

For visit-wise efficacy analyses, analysis time windows are constructed using the following algorithm:

1. Determine the nominal Rx day for each scheduled visit (e.g., Week 8 [8 weeks after baseline visit] equals Rx Day 57);
2. Determine the window around a specific nominal Rx day by adding or subtracting half of the interval between adjacent scheduled visits (e.g., days between Baseline and Week 8 is 56). The threshold between adjacent scheduled visits is determined by splitting the interval evenly between the visits.
3. If more than one assessment is included in a time window the assessment closest to the nominal day will be used. If there are two observations equidistant to the nominal day, the latest one will be used in analyses. If more than one assessment is included on the same day, then the worst assessment on that day will be used in analyses.
4. If a subject does not have an assessment in a particular visit window due to the inability to follow the visit schedule, but has assessments in the same study period both before and after the visit window, then the worst of the two will be used for the visit. Of note, this convention will be applied to the non-responder imputation method only.

Analysis windows have been specified for the analysis of efficacy, laboratory parameters, study drug injections and vital signs for efficacy and safety populations in [Table 3](#), [Table 4](#), [Table 5](#) and [Table 6](#). In order to include all post baseline data, the first post baseline interval starts on the day after the date of first study drug injection in each period (Rx Day 2) for all efficacy variables.

Table 3. Windows for High-Sensitivity C-Reactive Protein (hs-CRP; Safety Population)

Scheduled Week	Nominal Day (Rx Day)	Interval
Baseline	1	≤ 1
Week 24	169	2 ~ 337 ^a

a. Minimum of Rx Day 337 and 70 days after the last dose of study ADA.

Rx day relative to the maximum date of either the first dose of study ADA or the first dose of MTX during the study.

Table 4. Windows for All Other Efficacy and Safety Analyses (ITT/Safety Populations)

Scheduled Week	Nominal Day (Rx Day)	Interval
Baseline	1	≤ 1
Week 8	57	2 ~ 85
Week 16	113	86 ~ 141
Week 24	169	142 ~ 197 ^a

a. Minimum of Rx Day 197 and 70 days after the last dose of study ADA.

Rx day relative to the maximum date of either the first dose of study ADA or the first dose of MTX during the study.

Table 5. Windows for ADA Injection (Safety Population)

Scheduled Week	Nominal Day (Rx Day)	Interval
Baseline	1	≤ 1
Week 2	15	$2 \sim 22$
Week 4	29	$23 \sim 36$
Week 6	43	$37 \sim 50$
...
Week K	$K \times 7 + 1$	$K \times 7 - 5 \sim K \times 7 + 8$
Week 22	155	$149 \sim 162$

Rx day relative to the first dose date of study ADA during the study.

Table 6. Windows for MTX Administration (Safety Population)

Scheduled Week	Nominal Day (Rx Day)	Interval
Baseline	1	≤ 1
Week 1	8	$2 \sim 11$
Week 2	15	$12 \sim 18$
Week 3	22	$19 \sim 25$
...
Week K	$K \times 7 + 1$	$K \times 7 - 2 \sim K \times 7 + 4$
Week 23	162	$159 \sim 165$

Rx day relative to the first dose date of MTX during the study.

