### **8.1.4 Statistical Analysis of Efficacy**

The primary and secondary efficacy analyses will be conducted on the ITT population. The primary efficacy analyses will also be conducted for the following sub-populations:

- Subjects defined as primary sub-optimal responders at baseline, based on Investigator assessment;
- Subjects defined as secondary sub-optimal responders at baseline, based on Investigator assessment.

For the primary and secondary efficacy analyses, sub-optimal responder imputation (imputing missing satisfaction data as “dissatisfied”) will be used. In the event that greater than 5% of the satisfaction data are missing, the following will be carried out to impute the missing data in sensitivity analyses:

- Last observation carried forward (LOCF): The LOCF analyses will use the completed evaluation from the previous visit within the particular period for efficacy measures assessed, to impute missing data at later visits;

Additional exploratory efficacy outcomes will be analyzed using available data at each assessment point and changes over time for PASI, PGA and DLQI scores will be estimated using a Mixed Model. Exploratory analysis to determine associations between ADA serum levels and PASI, PGA and DLQI scores will also be carried out. This could be accomplished using a regression analysis with ADA serum level and visit as explanatory variables and either PASI, PGA or DLQI as response variables and controlling for within subject measurements. To determine the form of the regression model, the exploratory analyses could be carried out using LOESS Regression or general additive models. Alternatively, subjects could be grouped according to predetermined ranges of PASI, PGA or DLQI and the analysis could concentrate on determining differences in ADA serum levels in these groups.

---

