6.5 Missing Data Imputation

No global imputation is taking place at the database level. Efficacy and safety related imputations, as applicable, are outlined in Section 10.1 and Section 11.1, respectively.

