10.0 Efficacy Analysis

10.1 General Considerations

Point estimates and 95% confidence intervals (CIs) based on normal approximation will be provided for the discrete efficacy variables such as the proportion of responders to ADA/MTX. Change and percent change from baseline variables will be estimated using an appropriate estimation from a Mixed Model and statistical tests of change from baseline equal to zero will be carried out at the 0.05 significance level; 95% confidence intervals will also be provided.

Descriptive statistics will be provided. These include the number of observations, mean, and standard deviation for continuous variables and counts and percentages for discrete variables. Baseline and visit means at each scheduled visit will also be provided for change and percent change from baseline continuous variables.

Missing data will be imputed using the following methods for the efficacy analyses:

- Non-Responder Imputation (NRI): The NRI analysis will categorize any subject who has missing value at a specific visit as non-responder (or "dissatisfied" in satisfaction variables) for that visit. NRI will be the primary approach in analyses of categorical variables.
- Mixed-effect Model Repeat Measurement (MMRM): A mixed-effect model will be developed for continuous endpoint repeated measured at Baseline, Week 8, 16, and 24; controlling for time and subject ID. The fixed effects will be used to report the visit means at corresponding visits. Change and percent

change from baseline will be determined accordingly. MMRM will be the primary approach in analyses of continuous variables.

- Last Observation Carried Forward (LOCF): The LOCF analyses will use the completed evaluation from the previous visit to impute missing data at later visits. Baseline efficacy evaluations will not be carried forward. LOCF will be a sensitivity approach in analyses of continuous variables and categorical variables.

All efficacy variables will be analyzed for the ITT population overall, and separately by primary sub-optimal responders and secondary sub-optimal responders at baseline.

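### Does the worse-of-two convention for an empty Week 16 window undermine the non-responder rule for the primary endpoints?

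*SAP*

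**What the plan says.** Protocol 8.1.4 sets the missing-data rule: "For the primary and secondary efficacy analyses, sub-optimal responder imputation" is to be used, explained there as scoring missing satisfaction data as dissatisfied. LOCF is added as a sensitivity analysis if more than 5% of the satisfaction data are missing.

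SAP 6.5 tells the reader where to look: "Efficacy and safety related imputations, as applicable, are outlined in Section 10.1 and Section 11.1, respectively". SAP 10.1 then says: "The NRI analysis will categorize any subject who has missing value at a specific visit as non-responder". It adds that "NRI will be the primary approach in analyses of categorical variables" and that "LOCF will be a sensitivity approach in analyses of continuous variables and categorical variables".

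SAP 6.4, on analysis windows and data handling, contains a further convention as item 4. The trigger is that someone "does not have an assessment in a particular visit window due to the inability to follow the visit schedule". The remedy is worded for a person rated "both before and after the visit window, then the worst of the two will be used for the visit", with the two ratings drawn from one period of the study. Its scope is explicit: "this convention will be applied to the non-responder imputation method only". SAP Table 4 sets the Week 16 window at Rx Days 86 to 141.

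Protocol 8.1 leaves the full details of the analysis to the SAP.

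**The concern.** Take a subject who is highly or completely satisfied at Week 8 and at Week 24 and has no rating in the Week 16 window. The protocol rule makes this subject a Week 16 non-responder. Item 4 makes the subject a responder. SAP 6.5 points only to 10.1, and 10.1 does not mention item 4, so the plan seems to hold two rules for the same primary endpoints.

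The study has one arm, so the Week 16 proportion is itself the result and no between-group contrast could absorb a shift. Relative to the protocol rule, item 4 can only raise the proportion or leave it alone. LOCF, the only sensitivity approach described for categorical variables, carries the satisfied Week 8 rating forward and so agrees with item 4 for this subject. The sensitivity analysis would therefore not bring back the protocol figure. The primary analysis is also repeated in primary and secondary sub-optimal responders, where one subject weighs more.

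**Working it through.** **1. The plan's own precision figure.** Half-width = 1.96 × √(p(1−p)/N). At p = 0.30 and N = 50 this is 1.96 × √(0.21/50) = 12.7 points; at p = 0.50 it is 13.9 points. Both match SAP Table 2 and Protocol Table 5.

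**2. The window.** The cuts are (57 + 113)/2 = 85 and (113 + 169)/2 = 141, so the Week 16 window is Days 86 to 141, or 141 − 86 + 1 = 56 days. The protocol allows ±3 days, that is Days 110 to 116. To fall outside the analysis window, the visit must be at least 28 days early (113 − 85) or 29 days late (142 − 113).

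**3. Who is scored differently.** With Week 16 missing, let Week 8 and Week 24 each be missing or one of five ratings, which gives 6 × 6 = 36 patterns. Two of the five ratings count as satisfied.

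| Rule | Patterns scored as responder |
|---|---|
| Protocol 8.1.4, strict | 0 |
| SAP NRI with item 4 | 2 × 2 = 4 (satisfied on both sides) |
| LOCF | 2 × 6 = 12 (satisfied at Week 8), including all 4 above |

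The responder count is therefore ordered strict NRI ≤ item 4 ≤ LOCF. This takes the same study period to mean the treatment period, which SAP 4.2 describes separately from screening. If a screening rating could serve as the earlier value, the ordering against LOCF would need rechecking for the subject-rated endpoint.

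**4. Order of application.** Suppose 10.1 came first and scored every empty window as non-response. Item 4 is confined to NRI, so it would then have nothing left to act on. The order that gives both sections a meaning is item 4 first, then 10.1 on whatever is still missing.

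**5. Size.** Each subject turned into a responder adds 100/n points. The documents give no missed-visit rate, so the number of such subjects (k) is an assumption. At N = 50, starting from 15 responders:

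| k | Proportion | 95% CI (normal approximation) |
|---|---|---|
| 0 | 30.0% | 17.3 to 42.7 |
| 1 | 32.0% | 19.1 to 44.9 |
| 2 | 34.0% | 20.9 to 47.1 |
| 5 | 40.0% | 26.4 to 53.6 |

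From 25/50 = 50.0% (36.1 to 63.9), one subject gives 26/50 = 52.0% (38.2 to 65.8). At 30%, it would take seven such subjects to move the estimate by more than the planned half-width (12.7/2.0 = 6.35).

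Subgroup sizes are not given. For an assumed n of 40, 25 or 10, one subject adds 2.5, 4.0 or 10.0 points, against half-widths at 30% of 14.2, 18.0 and 28.4 points.

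**6. How plausible a case is.** Under Protocol 5.5.1 and Appendix H, the Week 8 supply covers the adalimumab doses of Weeks 8 to 14, and the next supply is handed out at Week 16. A subject with no visit through Day 141 would have no pens dispensed for the doses due at Weeks 16, 18 and 20 (Days 113, 127 and 141). The Week 20 dose could still be taken late under Protocol 5.5.4. If all three were skipped, Protocol 6.1.7 calls for a discussion of the subject's participation. The same subject would have to be highly or completely satisfied both before and after the gap. Subjects who leave with no later rating stay non-responders under every reading of NRI.

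**The case for a change.** The best reply is that item 4 is imputation placed in a windowing section. Items 1 to 3 define windows and choose among ratings observed inside them; item 4 acts only when a window is empty and brings in a value from outside. A reader who follows SAP 6.5 to 10.1 would not find it. Its trigger, an inability to keep to the schedule, is undefined, and deciding who qualifies in an open-label study with a subjective endpoint calls for judgement. The effect goes one way relative to the protocol, and no analysis named in the available text gives the strict figure.

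Part of this stands. SAP 10.1 lacks a cross-reference, the trigger phrase is loose, and the protocol does not anticipate the convention. The rest is weaker:

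- The rule is written down with its scope, in a SAP to be signed before database lock, and the protocol leaves such detail to the SAP. Protocol 8.1.4 sets no analysis windows, so the SAP has to say when a visit has a value.
- The trigger refers to attendance and not to the rating. If the subject attended and only the form was missed, it does not naturally apply.
- LOCF was planned as a less conservative check on NRI, and it still does that. It was not meant to recover strict NRI.
- SAP 10.2.2 plans the five satisfaction categories at all scheduled visits. If these are tabulated on observed data, which is not stated, the satisfied Week 16 count over the ITT number gives the strict figure. The list of tables is a separate document and was not available.

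**Conclusion.** No change to the plan follows. SAP 6.4 and 10.1 fit together when applied in the order that gives both an effect, and analysts would do this without further instruction. Strict NRI may slightly understate response in a subject who only missed a visit; item 4 corrects for that cautiously by taking the worse neighbouring rating, and it stays at or below LOCF. Either rule is defensible.

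The likely effect on the two Week 16 proportions is zero. If a case arises, it is worth 2.0 points at N = 50 against a half-width of 12.7 points at 30%, and more per subject in the subgroups, where the intervals are also wider. The primary endpoints are estimates with confidence intervals and carry no success threshold, so no decision turns on a shift of this size.

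This rests on three assumptions: very few subjects go 56 days around Week 16 without a rating and then return; the same study period means the treatment period; and the trigger is applied to attendance. A cross-reference from SAP 10.1 would be tidier, but the result does not depend on it.

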If a subject should forget to administer the ADA injection on their regularly scheduled dosing date, they should take the forgotten injection as soon as they remember the dose was missed up to the day before their next scheduled dose. The subject should not administer two ADA injections on the same day. If a subject should forget to take an MTX dose, they should take the forgotten dose as soon as they remember the dose was missed up to 3 days before their next scheduled dose. Subjects should be encouraged to record incorrect or missed ADA and MTX doses in their dosing diary. In the event the incorrect dose is taken or a dose is missed, the subject should be instructed to contact the site to determine how to proceed with dosing.

Doses not administered (e.g. not taken before next dose is scheduled), should be recorded as not taken in the source documents. The extra dose should be returned to the study site. The subject should resume their regular dosing schedule based on the first dosing date at Baseline.

The folic acid tablets will be provided by the Investigator at a dose of 1.0 mg per day. The required folic acid dose must be taken every day of the week except on the day when the MTX is taken. The Investigator will provide specific instructions on the number of folic acid tablets each subject should take.

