9.0 Study Drug Exposure and Compliance

Summary of study drug exposure and compliance will be provided.

The study drug exposure (days) will be summarized with the mean, standard deviation, minimum, first quartile, median, third quartile and maximum, for ADA and for MTX. Study drug exposure will be summarized as follows.

Study Drug Exposure (in Days) for ADA:

- Date of last study ADA injection – Date of first study ADA injection + 14 days.

Study Drug Exposure (in Days) for MTX:

- Date of last dose of MTX – Date of first dose of MTX + 7 days.

Compliance (%), which is defined as the number of injections received divided by the number of injections planned for ADA, and as the doses received divided by the doses planned for MTX, during the subject's participation in the study (rounded to 0.1%), will be summarized separately. In addition, at each scheduled time point, the number of ADA

injections and MTX doses received and compliance will be summarized with frequencies and percentages.

When computing compliance at each scheduled time point, the denominator for each week will include all subjects in each analysis population who have not prematurely discontinued prior to the scheduled study drug injection. The date of prematurely discontinuation will be taken from vital sign dataset.

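### SAP Table 5 closes each adalimumab dose window six days before the protocol's catch-up limit, so a permitted late injection is counted in the next week and by-time-point compliance shows a false miss

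*SAP*

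**What the plan says.** **Protocol 5.5.4, late doses.** For a missed ADA injection, subjects are told that "they should take the forgotten injection as soon as they remember the dose was missed up to the day before their next scheduled dose". For MTX, "they should take the forgotten dose as soon as they remember the dose was missed up to 3 days before their next scheduled dose". A late dose does not move the calendar: "The subject should resume their regular dosing schedule based on the first dosing date at Baseline". The same section says when a dose counts as missed: "Doses not administered (e.g. not taken before next dose is scheduled), should be recorded as not taken in the source documents".

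**SAP 6.4, dose windows.** The section states: "Analysis windows have been specified for the analysis of efficacy, laboratory parameters, study drug injections and vital signs". The ADA table is headed "Table 5. Windows for ADA Injection (Safety Population". Table 5 gives Week K of ADA the interval 7K−5 to 7K+8 around nominal day 7K+1, and its last row (Week 22) ends at Day 162. Table 6 gives Week K of MTX the interval 7K−2 to 7K+4, and its last row (Week 23) ends at Day 165. The day count for Table 5 is defined as "Rx day relative to the first dose date of study ADA during the study"; Table 6 counts from the first MTX dose in the same way.

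**SAP 9.0, compliance.** Overall compliance is doses received divided by doses planned. A second summary is by week: the sentence beginning "In addition, at each scheduled time point, the number of ADA" goes on to require injections, MTX doses and compliance as frequencies and percentages.

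The SAP has no rule for a dose taken late, for two doses in one window, or for a dose after the last window.

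**The concern.** The protocol and the SAP use different cut-offs for deciding which scheduled dose an injection belongs to. The protocol treats a dose as taken if it is given before the next one is due. Table 5 splits the interval at its midpoint. In the second half of the catch-up period the two disagree: the source record says the dose was taken, while the by-week table shows none for that week and an extra one for the next.

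At stake is the accuracy of a descriptive adherence table. A reader would see missed weeks and surplus injections for subjects who followed the protocol's catch-up instruction.

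**Working it through.** **Inputs**
- Nominal day of Week K: 7K+1 (SAP Tables 5 and 6).
- Dosing interval: 14 days for ADA, 7 days for MTX (Protocol 5.5.1 and Appendix H).
- After a late dose, the next dose stays on its nominal day (Protocol 5.5.4).
- Window formulas as in SAP Tables 5 and 6; the first post-baseline window opens on Day 2.

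**Step 1: reproduce the SAP rows**
- ADA: Week 2 closes at 14+8 = 22. Week 4 is 28−5 to 28+8 = 23 to 36. Week 6 is 42−5 to 42+8 = 37 to 50. Week 22 is 154−5 to 154+8 = 149 to 162.
- MTX: Week 1 closes at 7+4 = 11. Week 2 is 12 to 18. Week 3 is 19 to 25. Week 23 is 161−2 to 161+4 = 159 to 165.

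All eight stated rows match, and the windows are contiguous.

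**Step 2: ADA catch-up limit against window end**
- Next dose: 7(K+2)+1 = 7K+15. Last permitted day: 7K+14, which is nominal+13.
- Window end: 7K+8, which is nominal+7.
- Gap: 7K+9 to 7K+14, six days. Injections 8 to 13 days late leave their own week; those up to 7 days late stay in it.
- As a share of permitted late days this is 6/13 = 46%. It is not a share of doses.

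**Step 3: examples**

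| Dose | Due | Permitted to | Window ends | Late days outside | Filed under |
|---|---|---|---|---|---|
| Week 2 | Day 15 | Day 28 | Day 22 | 23–28 | Week 4 (23–36), with the dose due Day 29 |
| Week 4 | Day 29 | Day 42 | Day 36 | 37–42 | Week 6 (37–50), with the dose due Day 43 |

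A Week 2 injection on Day 28 followed by an on-time injection on Day 29 reads as 0 at Week 2 and 2 at Week 4.

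**Step 4: last ADA row**

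The Week 22 dose is due on Day 155 and its window ends on Day 162, with no row after it. An injection on Day 163 or later is in no window. No Week 24 dose is scheduled, so the protocol gives no catch-up limit here. If the 14-day interval is assumed to continue, the limit would be 155+13 = 168 and the uncovered days would be 163 to 168.

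**Step 5: MTX**

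The next dose is due on 7K+8, and three days before that is 7K+5 (nominal+4).
- If that day is included, the limit is 7K+5 against a window end of 7K+4: a one-day gap. For Week 1, 15−3 = Day 12, which Table 6 files under Week 2 (12–18).
- If that day is not included, the limit is 7K+4, exactly the window end: no gap.
- For Week 23 (due Day 162), assuming the interval continues and the day is included, the limit is 169−3 = 166 against a window end of 165.

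**Step 6: effect on the table**

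The documents give no rate of late doses, so this is an illustration. Assume 50 subjects, all still in the study and taking every dose, of whom r take the Week 4 injection 8 to 13 days late and the Week 6 injection on time.

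| r | Week 4 = (50−r)/50 | Week 6 = (50+r)/50 |
|---|---|---|
| 1 | 98% | 102% |
| 3 | 94% | 106% |
| 5 | 90% | 110% |

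Both weeks would be 100% if each dose were credited to the one it replaced. Overall compliance is 600/600 = 100% in every row (12 injections × 50 subjects).

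**The case against.** **Midpoint windows are a reasonable convention.** They follow the interval-splitting logic of SAP 6.4 and correctly describe when injections were given. That stands for a table of timing. SAP 9.0, however, labels the output compliance, and the protocol defines a missed dose by the next scheduled dose.

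**SAP 9.0 does not cite Tables 5 and 6.** True. The link is inferred from SAP 6.4, which says windows were set for study drug injections, and no other use of the tables is stated.

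**An existing rule might settle double entries.** SAP 6.4 keeps the assessment closest to the nominal day, but it is written for assessments in visit-wise efficacy analyses. Applied to doses, it would drop the late injection: the false double would go and the false miss would remain.

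**Long delays may be rare.** The Week 8 and Week 16 injections are given at clinic visits with a ±3-day window, and subjects are to contact the site about a missed dose. This stands. It leaves 11−2 = 9 post-baseline injections normally given at home, with no rate stated for any of them.

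**Stronger readings that the documents do not support.**
- A reader might infer that by-week compliance feeds the interpretation of response or of ADA levels. No section says so: efficacy uses the ITT population with no per-protocol set, the ADA-level analyses in Protocol 8.1.4 and 8.3 do not use weekly compliance, and the SAP places pharmacokinetics in separate documents.
- The 46% might be taken as a share of doses misfiled. It counts calendar days only.
- Two injections in one window might suggest a breach of the ban on same-day injections. A 14-day window implies nothing of the kind.

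**Conclusion.** The ADA inconsistency is real and does not depend on how any phrase is read. Each window closes six days short of the protocol's limit, so a permitted injection 8 to 13 days late is counted with the next dose. The false miss appears whether or not both doses in a window are counted; the false double appears only if both are.

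Two parts are conditional. The MTX gap is one day or none, depending on how the limit is read. For the final doses, it is certain that Tables 5 and 6 have no row after Days 162 and 165; that Days 168 and 166 are the permitted limits is an extrapolation.

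The consequence is minor. It is confined to the by-time-point compliance summaries, assuming these use Tables 5 and 6. Overall compliance, exposure days and the efficacy endpoints are unaffected. The actual size cannot be given, because the frequency of such late doses is not stated.

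**What to change.** Reconcile SAP Tables 5 and 6 with Protocol 5.5.4 before database lock. This concerns how doses are counted, not the catch-up rule itself.

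1. Where the diary or eCRF identifies the scheduled dose that a late dose replaces, assign it to that week. The protocol's diary description covers injection dates and times, MTX dosing and missed doses, so whether the link is recorded needs checking.
2. Otherwise, when a window holds two doses and the preceding window holds none, credit the earlier dose to the preceding week if it was taken before the next nominal dose day (ADA) or within the MTX catch-up limit. State whether that limit includes the third day before the next dose. For MTX, count dosing days, because Protocol 5.5.1 splits weekly doses above 10 mg into two on the same day.
3. Extend the last rows so that a late Week 22 ADA or Week 23 MTX dose is counted, and state the end day chosen.

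Step 2 is deliberately narrow. A rule that fills the earliest empty week would misfile an early dose after a true miss: with Week 2 missed and the Week 4 dose taken on Day 28, it would credit Week 2. Step 2 leaves that dose in Week 4. It does not resolve two long delays in a row, or a late dose followed by a true miss; those need the diary or a listing.

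The cost is SAP wording and slightly more complex derivation code, with no new data.
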